#### *Missing Event Dates Considerations:*

For adverse events with missing event date (i.e., mm/dd/yyyy), the safety and/or data management representatives will query sites for missing data. In the event that the date for adverse event is missing at the time of analysis, please reference Section 7.4 for the missing/partial date handling rules.

## 5 ADDITIONAL DATA ANALYSES

### 5.1 Interim Analyses

There is no formal interim analysis, but a descriptive summary of the study data may be made during the study, if needed.

### 5.2 Other Analyses

#### 5.2.1 Baseline Data Analyses

Subject demographics, medical history, EQ-5D-5L, Extended Prostate Cancer Index Composite (EPIC), PSA, CT and MRI will be summarized using descriptive statistics. For continuous variables, the descriptive statistics will include mean, standard deviation, minimum and maximum. For discrete variables, frequency tables will be displayed. No formal statistical testing will be performed.

#### 5.2.2 Post-procedure Analyses

Post-procedure information will be collected at 2 weeks, 6 weeks, 3 months and 10 months. And they will be summarized using descriptive statistics for continuous and frequency tables or proportions for discrete variables. No formal statistical testing will be performed.

#### 5.2.3 Patient disposition/status

Subject Disposition of follow-up Compliance will be provided at Post-procedure. A listing for deaths will be provided with relatedness to study device and radiation therapy, with date of death and duration of days from index procedure date.

#### 5.2.4 Analysis of Adverse and Serious Adverse Events

Frequency of site reported Serious adverse events and Non-serious adverse events associated with the study device will be summarized. The events will be summarized by MedDRA system organ class and MedDRA system preferred terms with event counts and proportions. A listing based on all site reported adverse events with seriousness, relationships and duration days will be created. Similarly, a listing for all anticipated/unanticipated adverse device events with seriousness and duration from onset date will be also produced.

For calculating events and rates, 'Events numbers' are total number of episodes for each type of event among all subjects. 'Rate of Subjects with Event' numbers are percent of subjects who experienced one or more episodes of the event. 'Events' numbers for "TOTAL" are the sum of the individual event category totals. 'Rate of Subjects with Event' numbers for "TOTAL" is the percent of subjects who experienced at least one adverse event.

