## 1 PROTOCOL SUMMARY

### 1.1 Study design

This study protocol is for the second part of SpaceOAR real world study in which long term follow-up visits will be performed (up to 1 year) outside Boao Medical Tourism Pilot Zone. The SpaceOAR real world study is a retrospective and prospective, single arm, observational study (Protocol of SpaceOAR RWS Windchill#: 92743236). Subjects with localized T1-T2 prostate cancer who have already been injected with the SpaceOAR and have received radiotherapy or will receive radiotherapy will be enrolled, and clinical data related to radiotherapy will be collected.

For subjects who have already completed radiotherapy before study kick-off, clinical data will be collected retrospectively, such as data related to radiotherapy, AE (if any) and MRI (if any). Follow up visit will be completed if applicable.

For subjects who receive therapy after study kick-off, follow up visits at 2 weeks, 6 weeks, 3 months and 10 months after radiotherapy will be scheduled to assess bowel, urinary and sexual function and quality of life.

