##### **3.1.2 Sample Size**

No formal sample size calculation is performed. The study plans to enroll up to 14 subjects.

To account for potential missing data in this retrospective and prospective study, a final sample size will be up to 20 subjects.

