#### **3.2 Secondary Endpoints**

- EPIC bowel and urinary assessment composite score at 2 weeks, 6 weeks, and 3 months post radiotherapy.
- EPIC sexual assessment composite score at 2 weeks, 6 weeks, and 3 months post radiotherapy.
- Quality of Life at 2 weeks, 6 weeks, and 3 months post radiotherapy (QOL).

- Whether there is SpaceOAR hydrogel between the posterior prostatic capsule and the anterior rectal wall at 6 weeks post radiotherapy.
- Whether the SpaceOAR hydrogel between the prostate and the anterior rectal wall is absorbed in 10 months post radiotherapy.
- Rectal adverse event (CTCAE).
- AEs/SAEs related to SpaceOAR hydrogel.

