### **3.2.2 Statistical Methods**

For continuous and ordinal variables, descriptive statistics will include number of observations, mean, standard deviation, minimum and maximum. Specific variables may also include additional statistics such as median, interquartile range (IQR) and confidence intervals. For binary or categorical variables, descriptive statistics will include percentage, numerator, denominator and number of missing observations if applicable. When the distribution of a variable does not support the use of parametric statistics, nonparametric approaches may be implemented. A parametric method of paired t-test or wilcoxon signed-rank non parametric test will be used for before and after clinical assessments.

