## **4 GENERAL STATISTICAL METHODS**

### **4.1 Analysis Sets**

The effectiveness set, and safety set include all subjects who have radiotherapy after injection of SpaceOAR hydrogel.

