### **7.3. Rules and Definitions**

For baseline categorical variables, subjects with missing values will not be counted in the corresponding denominators for proportions. Number of patients completing the visit will be considered in denominators.

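### SAP 5.2.4 reports AEs as a crude percent of subjects with no time point or allowance for time at risk; on the safety set this understates the 10-month rate

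*SAP*

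**What the plan says.** **AE rate.** SAP 5.2.4 defines the subject-level rates by saying that the "numbers are percent of subjects who experienced one or more episodes of the event". It gives no time point, person-time or censoring rule, and does not name the denominator. Its summary sentence reads "Frequency of site reported Serious adverse events and Non-serious adverse events associated with the study device will be summarized". Rectal AEs are not named there.

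**Rectal AEs.** "Rectal adverse event (CTCAE)" is a separate secondary endpoint in SAP 3.2, with no time point. Under SAP 3.2.2, for categorical variables, "descriptive statistics will include percentage, numerator, denominator and number of missing observations if applicable".

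**Two possible denominators.** SAP 4.1: "The effectiveness set, and safety set include all subjects who have radiotherapy after injection of SpaceOAR hydrogel". SAP 7.3, after a sentence on baseline categorical variables: "Number of patients completing the visit will be considered in denominators". The SAP does not say which one governs AE rates.

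**Follow-up.** For men treated after kick-off, SAP 1.1 states that "follow up visits at 2 weeks, 6 weeks, 3 months and 10 months after radiotherapy will be scheduled", and the schedule in SAP 1.6 collects AEs through the 10-month visit. For men who finished RT earlier, SAP 1.1 provides follow-up only where applicable. Protocol section 13 does not treat missing data or tests as deviations for retrospectively collected data. SAP 3.1.2 expects gaps: "To account for potential missing data in this retrospective and prospective study, a final sample size will be up to 20 subjects".

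**The concern.** Rectal AEs and hydrogel-related AEs/SAEs are the study's two safety endpoints, and SAP section 2 allows the analyses to be used in regulatory submissions. A reader will take an AE percentage from a study with 10 months of follow-up as the risk through 10 months. A crude percent over the safety set answers a different question: the share of men with an event seen during whatever follow-up each man had. Someone last assessed at 3 months without an event counts the same as someone seen event-free at 10 months.

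The timing matters for the rectal endpoint. Protocol section 4.1 says late rectal symptoms may take 6 to 12 months to appear, so short follow-up would miss late events more than acute ones.

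Nothing else in the SAP adjusts for this. SAP 4.3 deals with missing values and SAP 7.4 with missing AE dates. AEs are recorded when they occur, so a man no longer followed has no AE record, which looks the same as having no event. The number missing under SAP 3.2.2 will not pick him up unless the plan defines who is evaluable.

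**Working it through.** **Nothing to reproduce.** The documents give no AE rate, dropout rate or safety threshold. The nearest figure is the rise from 14 to 20 subjects in SAP 3.1.2. It implies (20 − 14)/20 = 30%, but that is back-solved from a general missing-data allowance. It is used below only as the top of a range.

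**Formula, safety-set denominator.** Let p be the true 10-month risk, d the share of men with truncated follow-up, and f the share of those men's events that fall after truncation. Truncation is assumed unrelated to risk. Fully followed men contribute (1 − d)p and truncated men contribute d·p(1 − f), so

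expected crude rate = (1 − d)p + d·p(1 − f) = p(1 − d·f).

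A man with an event before he leaves still counts; only event-free truncation matters.

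| p | d | f | crude rate |
|---|---|---|---|
| 10% | 10% | 0.5 | 9.5% |
| 10% | 30% | 0.1 (mostly early events) | 9.7% |
| 10% | 30% | 0.5 | 8.5% |
| 10% | 30% | 1 (extreme) | 7.0% |
| 20% | 10% | 0.5 | 19.0% |
| 20% | 30% | 0.5 | 17.0% |
| 20% | 30% | 1 (extreme) | 14.0% |

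**Simulation of the alternatives.** Settings: 20 men, constant hazard, uniform loss unrelated to events, 20,000 replicates.

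| p | d | crude, all men | 1 − Kaplan-Meier | completers' events / completers | all events / completers |
|---|---|---|---|---|---|
| 10% | 10% | 9.55% | 10.04% | 10.06% | 10.64% |
| 10% | 30% | 8.55% | 10.02% | 10.00% | 12.38% |
| 20% | 10% | 19.08% | 20.04% | 20.00% | 21.26% |
| 20% | 30% | 17.15% | 20.05% | 20.03% | 24.88% |

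The crude rate is low and the Kaplan-Meier estimate is close to the truth. A completer denominator gives no bias if only completers' events are counted, and an upward bias if all events are.

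**An evaluable denominator is not a remedy.** Suppose the denominator is men with an event plus men followed event-free to 10 months. With p = 20%, d = 30%, f = 0.5, the events are 0.20 × (1 − 0.15) = 0.17 and the event-free completers are 0.70 × 0.80 = 0.56. The rate is 0.17/(0.17 + 0.56) = 23.3%, too high by about as much as the crude 17.0% is too low.

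**Against sampling error.** At N = 20 one man is 5 points. Two events in 20 is 10.0%, with an exact 95% interval of 1.2% to 31.7%. The shortfall at p = 10% is 0.5 point (d = 10%, f = 0.5) to 3 points (d = 30%, f = 1), well inside that.

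**The case against.** **The denominator is not stated, so a downward bias cannot be asserted.** This stands in part. A reader might infer that the plan classes lost men as event-free and that its safety rates are therefore too low. No section says so, and SAP 7.3 could lead to no bias or an upward one. The safety set is still the more natural reading: SAP 5.2.4 counts episodes over all subjects, the SAP 7.3 sentence follows a rule for baseline variables, and a one-or-more-episodes rate belongs to no single visit. The understatement is conditional on that reading.

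**SAP 5.2.4 does not govern the rectal endpoint.** Its summary sentence is limited to device-associated events, although its TOTAL row refers to any adverse event. The rectal endpoint falls under SAP 3.2.2, which adds a missing count but no time point or evaluability rule. The gap is the same.

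**The size could be overstated.** A reader might take 30% as the expected dropout, or apply the 5-24% chronic toxicity in Protocol section 4.1 to these men. Neither is supported. The 30% is back-solved. The 5-24% is Grade 2 or higher toxicity with dose-escalated IMRT, not a spacer rate and not a 10-month rate. The same section quotes 2% (grade 1+) and 0% (grade 2+) at 3 years with the spacer. At p = 2%, d = 30%, f = 1 the shortfall is 2% × 0.30 = 0.6 point, or 0.12 of a man in 20. Hydrogel events are probably less exposed, because injection precedes RT and the gel clears in about six months.

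**Follow-up is already visible.** SAP 5.2.3 reports follow-up compliance, SAP 5.2.4 lists all AEs, and SAP 7.4 records missed visits as deviations. A crude rate beside a disposition table is a conventional display in a small descriptive study. That keeps the point minor, but none of these outputs adjusts the rate.

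**Conclusion.** The point holds as a conditional one. SAP 5.2.4 reports a crude percent with no time point and no allowance for time at risk. If it is divided by the safety set, the 10-month rate is understated by the factor (1 − d·f). Follow-up is unequal by design through the retrospective subjects, even before any withdrawals.

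Under the assumed ranges, a true 10% would be reported as between 9.5% and 7.0%. The bias is near zero when events are acute and probably small for hydrogel events. It is small beside the sampling error at 20 men or fewer. These figures rest on assumed p, d and f, and on truncation unrelated to risk; the documents supply none of them.

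No study conclusion turns on this, since there is no safety hypothesis or threshold. It is a modest, inexpensive improvement to how the two safety endpoints are reported.

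**What to change.** In SAP 5.2.4:

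1. Keep the crude table and name the safety set as its denominator.
2. State that the visit-completer denominator in SAP 7.3 does not apply to cumulative AE rates.
3. For rectal AEs and for hydrogel-related AEs/SAEs, add the cumulative incidence at 3 and 10 months after RT: 1 minus Kaplan-Meier, or Aalen-Johansen with death as a competing event. Censor each man at his last AE assessment. State when the clock starts, since AEs are also collected before and during RT.
4. Show the number still under AE follow-up beside each estimate. The 10-month visit may fall 30 days early, so define that count with the visit window in mind.
5. Do not use a denominator of men with events plus completers, which is biased upward.

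The cost is a few sentences and one extra table from dates already collected, with no new patients or visits. Intervals will be wider, and with few events the censored estimate will be imprecise. It also assumes that truncation is unrelated to risk.

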### **5.2.5 Protocol Deviations**

Deviations from Investigational Protocol collected during procedure and post procedure for all the planned events as specified in protocol will be captured and summarized. A table summarized with counts and percent and another summary table presented based on deviations reasons will be presented. A listing will be provided with deviation type, reason, visit and assessment/procedure requirement during the study for all subjects.

### **5.2.6 Device Deficiencies**

A table will be produced for device deficiencies with count and percent by deficient components. A supported listing will be provided by subject, and if its leading to any event.

## **5.3 Changes to Planned Analyses**

Any changes to the planned statistical analyses made prior to performing the primary endpoint analysis will be documented in an amended Statistical Analysis Plan which will be approved prior to performing the analysis. Changes from the planned statistical methods after performing the analysis will be documented in the clinical study report along with a reason for the deviation.

## **6 VALIDATION**

All clinical data reports generated per this plan will be validated per 90702587, Global WI: Clinical Data Reporting Validation. The validation level R1 chosen for all primary, secondary, safety and other additional endpoints. The validation program includes checking logs and generating compare reports in comparing with main programming datasets. Statistical analyses and validation will be performed by IQVIA team.

## **7 PROGRAMMING CONSIDERATIONS**

All statistical programming tasks will be performed by IQVIA™ independently.

### **7.1. Statistical Software**

All statistical analyses will be done using The SAS System Version 9.2 software or above (Copyright © 2000 SAS Institute Inc., [name]. All rights reserved.).

### **7.2. Format of Output**

Statistical analysis will be performed using SAS. All output for the final statistical report will be in the form of a Word document, which may include tables, figures, graphs, and listings, as appropriate.

### **7.3. Rules and Definitions**

For baseline categorical variables, subjects with missing values will not be counted in the corresponding denominators for proportions. Number of patients completing the visit will be considered in denominators.

### **7.4. Handling of Missing/Partial Date**

Missed or late visits will be recorded as Protocol Deviations.

When calculating rates of all adverse events, both device and/or procedure related with missing event date (i.e. mm/dd/yyyy), every effort should be made to work with safety and/or data management representatives to query sites for missing data. However, in the situations when it cannot be resolved, missing and partial missing dates may be handled as using the worst-case scenario as follows:

Partial Date Description	Action taken
Entire onset date is missing	The procedure date will be used for the onset date.
The month and the day of the month are missing but the year is available	January 1st will be used for the month and day of the onset date. However, if the imputed date falls before the procedure date, then the procedure date will be used for the onset date.
Day is missing, but the month and year are available	The 1st will be used as the day of the onset date. However, if the imputed date falls before the procedure date, then the procedure date will be used for the onset date.
